8.2.2. Height and Weight

Height and weight will be measured and recorded, and BMI calculated.

8.2.3. Pregnancy Testing

Urine pregnancy testing will be conducted at the screening, baseline, and study exit visits. Females of childbearing potential must have a negative test result before receiving the study intervention. This test may also be performed at any other visit, at the investigator's discretion. At each visit, the investigator should discuss contraceptive use compliance with females of childbearing potential.

8.2.4. Oral Examination

As referenced in Exclusion criterion 4.07, oral examinations will be conducted at the Screening Visit, in order to rule out other potential etiologies for MMP, such as malignancy. The investigator will assess extraorally for parotid gland tumors, parotiditis (gland or duct), lipoma, sialolith (stones), or osseous remodeling at the gonial angle including bone protrusion, and intraorally for osseous lesions in the angle of the mandible behind the molars, or for expansion of

alveolar bone supporting the teeth. The examination procedures are described in greater detail in the Study Manual.

8.2.5. Screening for TMJD

Screening for signs/symptoms of possible TMJD will be conducted by the investigator at the Screening Visit, as described in the Study Manual. Depending on the findings, the investigator may decide to exclude the participant from the study (per exclusion criterion 4.02), or may refer the participant to a dentist for further TMJD screening, to be completed prior to Day 1. The participant may complete the rest of the planned activities and procedures for the Screening Visit, with the dentist examination occurring at a later time in the screening period. If, based on findings from a dental examination, the dentist diagnoses the participant with TMJD, the participant will be considered a screen failure.

8.3. Adverse Events and Serious Adverse Events

The definitions of an AE or SAE can be found in Appendix 2.

AEs will be reported by the participant (or, when appropriate, by a caregiver, surrogate, or the participant's legally authorized representative).

The investigator and any qualified designees are responsible for detecting, documenting, and recording events that meet the definition of an AE or SAE and any other study-specific terms as relevant and remain responsible for following up AEs that are serious, considered related to the study intervention or study procedures, or that caused the participant to discontinue the study intervention or study (see Section 7).

8.3.1. Time Period and Frequency for Collecting Adverse Event and Serious Adverse Event Information

All AE/SAEs from the signing of the ICF will be collected at the timepoints specified in the SoA and as observed or reported spontaneously by study participants.

Medical occurrences that begin before the start of study intervention, but after obtaining informed consent will be recorded in the AE section of the eCRF and will be considered pretreatment AEs.

All SAEs will be recorded and reported to the sponsor or designee within 24 hours, as indicated in Appendix 2. The investigator will submit any updated SAE data to the sponsor within 24 hours of it being available.

Investigators are not obligated to actively seek AE or SAE information after conclusion of the study participation. However, if the investigator learns of any SAE, including a death, at any time after a participant has been discharged from the study, and he/she considers the event to be

reasonably related to the study intervention or study participation, the investigator must promptly notify the sponsor.

The method of recording, evaluating, and assessing causality of AEs and SAEs and the procedures for completing and transmitting SAE reports are provided in Appendix 2.

8.3.2. Method of Detecting Adverse Events and Serious Adverse Events

Care will be taken not to introduce bias when detecting AEs and/or SAEs. Open-ended and non-leading verbal questioning of the participant is the preferred method to inquire about AE occurrences.

8.3.3. Follow-up of Adverse Events and Serious Adverse Events

After the initial AE/SAE report, the investigator is required to proactively follow each participant at subsequent visits/contacts. All SAEs and AESIs as defined in Appendix 2 will be followed until resolution, stabilization, the event is otherwise explained, or the participant is lost to follow-up (as defined in Section 7.3).

The investigator is obligated to perform or arrange for the conduct of supplemental measurements and/or evaluations as medically indicated or as requested by the sponsor to elucidate the nature and/or causality of the AE or SAE as fully as possible. This may include additional laboratory tests or investigations, histopathological examinations, or consultation with other health care professionals.

If a participant dies during participation in the study or during a recognized follow-up period, the investigator will provide the sponsor with a copy of any postmortem findings including histopathology.

New or updated information will be recorded in the originally completed eCRF.

The investigator will submit any updated SAE data to the sponsor within 24 hours of receipt of the information.

8.3.4. Regulatory Reporting Requirements for Serious Adverse Events

- Prompt notification by the investigator to the sponsor of an SAE is essential so that legal obligations and ethical responsibilities towards the safety of participants and the safety of a study intervention under clinical investigation are met.
- The sponsor has a legal responsibility to notify both the local regulatory authority and other regulatory agencies about the safety of a study intervention under clinical investigation. The sponsor will comply with country-specific regulatory requirements relating to safety reporting to the regulatory authority, IRBs/ IECs, and investigators.

- Investigator safety reports must be prepared for suspected unexpected serious adverse reactions (SUSARs) according to local regulatory requirements and sponsor policy and forwarded to investigators as necessary.
- An investigator who receives an investigator safety report describing an SAE or other specific safety information (eg, summary or listing of SAEs) from the sponsor will review and then file it along with the investigator's brochure and will notify the IRB/IEC, if appropriate according to local requirements.

8.3.5. Pregnancy

- If a pregnancy is confirmed after the participant has received the study intervention, the participant may choose to exit the study after appropriate safety follow-up or to remain in the study for all safety and efficacy follow-up assessments through the end-of-study visit.
- Details of all pregnancies in female participants will be collected from the signing of the ICF and through the duration of the pregnancy.
- If a pregnancy is reported, the investigator should inform the sponsor within 24 hours of learning of the pregnancy and should follow the procedures outlined in Appendix 6.
- Abnormal pregnancy outcomes (eg, spontaneous abortion, fetal death, stillbirth, congenital anomalies, ectopic pregnancy) are considered SAEs.

8.3.6. Protocol-Specific Adverse Events

The investigator should refer a participant to a qualified dentist for further evaluation in the case of severe (as defined in Appendix 2) mastication disorders (eg, severe reports of chewing weakness, abnormal chewing, difficulty chewing). For any referral, the investigator must obtain findings from the dentist for complete AE documentation in the eCRF.

8.3.7. Adverse Events of Special Interest

AESI will be reported as indicated in Appendix 2.

8.3.8. Medication Errors

Medication error refers to any unintended error in the dosing and/or administration of the study intervention as per instructions in the protocol, for example:

- Wrong study intervention
- Wrong dose (including dosing regimen, concentration, amount)
- Wrong participant (ie, not administered to the intended participant)

8.4. Treatment of Overdose

The LD₅₀ for BOTOX in humans is estimated from primate studies to be approximately 3000 U. This makes accidental injection of a lethal dose highly unlikely, but significant AEs may still occur at doses below the LD₅₀ (Herrero 1967, Scott 1989).

Excessive doses may produce local or distant, generalized, and profound neuromuscular paralysis. Should accidental injection or oral ingestion occur or overdose be suspected, the participant should be medically monitored for up to several weeks for progressive signs or symptoms of systemic muscular weakness that could be local or distant from the site of injection, and which may include ptosis, diplopia, dysphagia, dysarthria, generalized weakness, or respiratory failure. Please refer to the general Section 6.5 of the BOTOX MMP investigator's brochure for further details.

In the event of an overdose, the investigator should:

- 1. Contact the medical safety physician immediately.
- 2. Closely monitor the participant for AEs and SAEs.
- 3. Document the quantity of the excess dose as well as the duration of the overdose in the eCRF as well as other details that led to the overdose.

8.5. Pharmacokinetics

PK parameters are not evaluated in this study.

8.6. Pharmacodynamics

Pharmacodynamic parameters are not evaluated in this study.

8.7. Genetics

Genetics are not evaluated in this study.

8.8. Biomarkers and Other Assessments

Biomarkers are not evaluated in this study.

8.9. Health Economics

Health economics parameters are not evaluated in this study.

9. Statistical Considerations

9.1. Statistical Hypotheses

The following set of hypotheses will be used to compare the BOTOX groups with placebo:

- Null hypothesis: BOTOX and placebo are equally effective in reducing MMP as measured by the proportion of responders achieving MMPS Grade ≤ 3 at Day 90.
- Alternative hypothesis: BOTOX and placebo are not equally effective in reducing MMP as measured by the proportion of responders achieving MMPS Grade ≤ 3 at Day 90.

9.2. Sample Size Determination

The primary efficacy parameter is the proportion of responders who achieve MMPS Grade \leq 3 at Day 90. Based on previous data from Study 191622-130 and the assumption of a difference of \geq 34% in MMPS responder rate between BOTOX 48 U or 72 U and placebo group, approximately 50 participants per study intervention group will provide > 90% power using a 2-sided Mantel-Haenszel test, 10% dropout rate, and 5% significance level.

Approximately 225 participants will be screened to achieve 150 enrolled to study intervention and 135 evaluable participants for an estimated total of 45 evaluable participants per intervention group.

9.3. Populations for Analyses

The analysis populations will consist of participants as defined below:

- The mITT population includes all randomized participants with ≥ 1 postbaseline MMPS assessment. Participants will be summarized according to the randomized study intervention.
- The safety population includes all treated participants who receive ≥ 1 administration of study intervention. Participants will be summarized according to the study intervention they actually received.

9.4. Statistical Analyses

The SAP will be developed and finalized before database lock and unblinding and will describe the participant populations to be included in the analyses, and procedures for accounting for missing, unused, and spurious data. This section is a summary of the planned statistical analyses of the primary and secondary endpoints.

9.4.1. Efficacy Analyses

The efficacy analyses will be based on the mITT population. The last-observation-carried-forward approach will be used to impute missing postbaseline values. Baseline for efficacy is defined as the last nonmissing efficacy assessment before the first dose of study intervention. All statistical tests will be 2-sided hypothesis tests performed at the 5% level of significance for main effects.

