4.2. Scientific Rationale for Study Design

In the current study, all participants will be assessed for a minimum of 180 days after double-blind study intervention on Day 1. A randomized double-blind design minimizes investigator and participant bias and the placebo control provides a comparator. Previous studies, including Allergan's Study 191622-130, reported peak efficacy of botulinum toxin treatment of MMP at 3 months (Hong 2005, Kim 2003, Kim 2007, Park 2003), therefore, Day 90 has been chosen as the primary timepoint in the present study. In Study 191622-130, statistically significant effects were lost for most efficacy measures after 6 months; therefore, a follow-up period of 180 days is considered appropriate for this Phase 2b study.

Allergan developed the MMPS, a clinician's assessment tool for evaluation of MMP. In the present study, the MMPS is to be used by trained clinicians to evaluate and grade the prominence of the masseter muscle on the left and right sides of the face as the primary endpoint measure. The MMPS is a static measurement encompassing both visual and palpable examination of the masseter muscle at rest and at jaw-clench state. The MMPS showed substantial inter- and intrarater reliability in the nontreatment scale validation Study 191622-128, confirming its acceptability for use in the present study. Study 191622-130 was the first study to use the MMPS to assess the treatment effect of BOTOX and it demonstrated statistically significant greater proportions of responders in achieving both a MMPS Grade ≤ 3 , and ≥ 1 -grade or ≥ 2 -grade improvements from baseline, as assessed by the investigator at the primary timepoint. Results from Study 191622-130 support a clinician tool (MMPS) that can immediately assess the relevant masseter prominence without requiring radiological exposure from CT scans or 3D standardized imaging that requires a trained photo analyst to confirm the aesthetic complaint described by the participant.

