4.3. Justification for Dose

In Allergan's Phase 2 Study 191622-130, participants received total doses ranging from BOTOX 24 U to 96 U. For the primary and key secondary endpoints (at Day 90), statistically significant positive efficacy results were demonstrated for all 4 BOTOX doses, with a dose-dependent trend favoring the higher 3 doses (48 U, 72 U, and 96 U), which produced statistically significant changes in MMP compared with placebo. The benefits of 72 U and 96 U were similar for duration (approximately 9 months for Kaplan-Meier median time to loss of 1-grade MMPS response), volume reduction, MMPS Grade change, facial width, facial angle, and facial shape. There was no additional benefit demonstrated with 96 U over 72 U. Statistically significant efficacy results were also obtained with the 24 U dose versus placebo for the majority of endpoints evaluated, though not all. However, the Kaplan-Meier duration of effect based on median time to loss of MMPS 1- or 2-grade improvement was approximately 3 to 7 weeks shorter in the BOTOX 24 U group than the BOTOX 48 U group.

The proportion of responders achieving a rating of \leq 3 (moderate) on the MMPS was significantly greater with all BOTOX doses compared with placebo (p < 0.008), with the greatest impact shown in the 48 U (83.3%), 72 U (89.5%), and 96 U (89.5%) dose groups at Day 90.

Participants treated with BOTOX experienced significant reductions in lower facial volume (cm³) at Day 90 compared with placebo (p < 0.001), with the greatest mean reductions shown in the 3 highest BOTOX dose groups of 48 U (-6.84 cm³), 72 U (-7.41 cm³), and 96 U (-8.20 cm³).

The responder rate for achieving a 2-grade improvement from baseline using the MMPS was significantly greater with all BOTOX doses compared with placebo (p < 0.001), with the greatest proportion of responders in the 72 U (73.7%) and the 96 U (65.8%) dose groups at Day 90; the proportion of responders in the 48 U dose group was 47.2%.

BOTOX administration was shown to be safe through Day 360 for all doses (24 U, 48 U, 72 U, and 96 U). Facial paresis (including reports of weak or altered smile) was reported in the highest dose group (96 U) as a local effect.

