9.1 PRIMARY EFFICACY PARAMETER

The primary efficacy variable is the investigator's assessment of MMP using the MMPS (1 = minimal, 2 = mild, 3 = moderate, 4 = marked, 5 = very marked). Each participant's MMPS score will be based on the worst score of the left and right side of the face. If a score is missing for 1 side of the face, then the participant's MMPS score will be based on the score for the other side of the face. The primary efficacy endpoint will be the proportion of responders who achieve MMPS Grade ≤ 3 at Day 90.

The following set of hypotheses will be used to compare the BOTOX groups with placebo:

- Null hypothesis: BOTOX and placebo are equally effective in reducing MMP as measured by the proportion of responders achieving MMPS Grade ≤ 3 at Day 90.
- Alternative hypothesis: BOTOX and placebo are not equally effective in reducing MMP as measured by the proportion of responders achieving MMPS Grade \leq 3 at Day 90.

Frequency counts of participants achieving a MMPS Grade \leq 3 will be tabulated by study intervention group at each postbaseline visit. The difference between each BOTOX dose and placebo in the proportion of participants with MMPS \leq 3 will be analyzed using Cochran-Matel-Haenszel (CMH) model stratified by baseline MMPS Grade (4 or 5).

A sensitivity analysis will be performed based on all observed data for the mITT Population.

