9.2 SECONDARY EFFICACY PARAMETERS

The following are considered secondary endpoints at Day 90:

- Proportion of responders who achieve MMPS-P Grade ≤ 3
- Proportion of responders who achieve \geq 2-grade MMPS improvement from baseline

- Proportion of responders who achieve \geq 2-grade MMPS-P improvement from baseline
- Proportion of responders who achieve PSAC Grade ≥ 2 (at least moderately improved from baseline)
- Change from baseline in lower facial volume by VECTRA M3 measured using landmark area of interest (AOI) and statistical MMP AOI

For all the responder analyses, frequency counts of responders for each of the responder definitions above will be tabulated by study intervention group at each postbaseline visit. The difference between each BOTOX dose and placebo in the proportion of responders will be analyzed using CMH model stratified by baseline MMPS Grade (4 or 5).

The change from baseline in lower facial volume using both landmark AOI and statistical MMP AOI will be analyzed using analysis of covariance (ANCOVA) with study intervention and investigator site as factors and baseline MMPS Grade (4 or 5) as a covariate. Missing values for change from baseline in lower facial volume at Day 30 will be imputed using the average of participants with non-missing values.

Summary statistics for each endpoint will be tabulated by study intervention group at each postbaseline visit.

Each of the responder analyses will be analyzed using CMH model stratified by baseline MMPS grade.

The change from baseline analyses will be analyzed using ANCOVA with study intervention and investigator site as factors and baseline MMPS grade and baseline score as covariates.

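### Last observation carried forward has no visit limit, so it can overstate how long the BOTOX effect lasts, chiefly at Day 180

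*Protocol*

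**What the plan says.** Protocol 9.4.1 sets the missing-data rule for efficacy: "The last-observation-carried-forward approach will be used to impute missing postbaseline values". SAP 9.0 repeats it. Neither limits it to a visit. SAP 9.2 adds an exception for lower facial volume: a missing Day 30 change is replaced by the average of the participants who have one. That exception is needed only if carry-forward runs visit by visit, because no earlier change value exists to carry to Day 30.

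SAP 9.1 says that counts of participants at MMPS Grade 3 or below "will be tabulated by study intervention group at each postbaseline visit", and SAP 9.2 does the same for the secondary responder endpoints. The text under SAP 9.2 adds: "Summary statistics for each endpoint will be tabulated by study intervention group at each postbaseline visit". The windows in SAP 14.1 include Days 120, 150 and 180.

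Protocol 4.2 describes the expected time course. Earlier studies "reported peak efficacy of botulinum toxin treatment of MMP at 3 months", and in Study 191622-130 "statistically significant effects were lost for most efficacy measures after 6 months".

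SAP 9.1 plans one sensitivity analysis on observed data, under the MMPS parameter and without naming visits. None is visible for MMPS-P, PSAC or lower facial volume.

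**The concern.** Carry-forward assumes that a participant's state does not change after the last assessment. For a treatment whose effect rises to a peak and then fades, that assumption fails after the peak. A BOTOX responder last seen near Day 90 remains a responder in the Day 180 table whatever would have happened. Placebo participants have no drug effect to lose, so the error falls mainly on the BOTOX arms and, for these leavers, in their favour.

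The late visits are where the trial shows persistence and waning. Protocol 4.2 justifies the 180-day follow-up by loss of effect, and Protocol 4.3 cites duration of effect among the reasons for the doses chosen. A late time course that is held up artificially, or held up differently in the 48 U and 72 U arms because late dropout differs, would mislead on that question.

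**Working it through.** **The plan's own figures.** The documents give no figure for the late visits. The nearest are dropout and power in Protocol 9.2. Dropout reproduces: 150 x 0.90 = 135, or 45 per group. Power reproduces too. With 45 per group, a 34-point difference and a 2-sided 5% test, an unstratified two-proportion calculation gives at least 91.1% at any placebo rate between 5% and 65% (lowest near 33% versus 67%), against a stated figure above 90%. The 10% dropout is used below.

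**Inputs from the documents.** Day 90 responder rates in Study 191622-130 (Protocol 4.3): "48 U (83.3%), 72 U (89.5%), and 96 U (89.5%) dose groups at Day 90". Planned dropout: 10%.

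**Assumptions.**
- 50%, 70% or 85% of the Day 90 rate remains at Day 180.
- Leavers would have followed the same course as stayers.
- Placebo does not shift.

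**Formula.** Error at visit t = sum over last visits s of (share last seen at s) x (rate at s - true rate at t).

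**Case 1: all 10% leave after Day 90, with Day 90 as the last value.** Error at Day 180 = 0.10 x Day 90 rate x (1 - fraction remaining).

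| Fraction remaining | 48 U | 72 U |
|---|---|---|
| 50% | 0.10 x 83.3 x 0.50 = 4.2 points | 0.10 x 89.5 x 0.50 = 4.5 points |
| 70% | 0.10 x 83.3 x 0.30 = 2.5 points | 0.10 x 89.5 x 0.30 = 2.7 points |
| 85% | 0.10 x 83.3 x 0.15 = 1.2 points | 0.10 x 89.5 x 0.15 = 1.3 points |

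If 5% leave after Day 90, these halve.

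**Case 2: the 10% is spread evenly**, 2% last seen at each of Days 30, 60, 90, 120 and 150. Further assumptions: the Day 30 rate is 40% to 80% of peak, Day 60 lies halfway between Day 30 and Day 90, and the decline from Day 90 to Day 180 is linear.

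- Highest Day 180 result (72 U, 50% remaining, Day 30 at 80% of peak). The rates at the five last visits are 71.6, 80.55, 89.5, 74.58 and 59.67, against a true 44.75. Error = 0.02 x (26.85 + 35.80 + 44.75 + 29.83 + 14.92) = +3.0 points.
- Lowest Day 180 result (72 U, 85% remaining, Day 30 at 40% of peak). The rates are 35.8, 62.65, 89.5, 85.03 and 80.55, against a true 76.08. Error = 0.02 x (-40.28 - 13.43 + 13.43 + 8.95 + 4.48) = -0.5 points.

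Range over all combinations and both doses:

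| Visit | Net error, points |
|---|---|
| Day 120 | -1.3 to +0.4 |
| Day 150 | -1.0 to +1.6 |
| Day 180 | -0.5 to +3.0 |

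**Volume, under Case 1 with half the effect remaining (assumed).** Protocol 4.3 gives -6.84 cm³ (48 U) and -7.41 cm³ (72 U) at Day 90. The reduction is overstated by 0.10 x (6.84 - 3.42) = 0.34 cm³ and 0.10 x (7.41 - 3.705) = 0.37 cm³, about 10% of the assumed Day 180 effect.

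**Scale.** With 50 per group, an assumed placebo rate of 30% and a BOTOX rate of 60%, the standard error of the difference is sqrt(0.60 x 0.40/50 + 0.30 x 0.70/50) = 9.5 points.

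**The case against.** A reader might infer that Days 120, 150 and 180 are all overstated. The documents do not support that. Only participants last seen near Day 90 are held at the peak. Those last seen at Day 30 or 60 may carry pre-peak values, which works against BOTOX, and those last seen at Day 120 or 150 carry partly waned ones. Protocol 7.2 asks for every effort to obtain an exit visit, which can supply a later value. This stands, and it makes the sign at Days 120 and 150 uncertain. The exit visit is not a full remedy: SAP 14.1 assigns visits by actual day, so an exit on Days 76 to 105 becomes the Day 90 value and is then carried forward.

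The evidence on waning is limited. Loss of significance after 6 months falls beyond this trial's last visit and says nothing exact about Day 180. Protocol 4.3 reports, for 72 U and 96 U, "approximately 9 months for Kaplan-Meier median time to loss of 1-grade MMPS response". For a participant with baseline Grade 4, a 1-grade improvement is the same as reaching Grade 3, so more than half of such responders at 72 U might still respond at Day 180. The 50% row is therefore pessimistic for them. The figure does not settle the matter for 48 U, or for baseline Grade 5, where the primary response needs two grades.

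The error is small against a standard error of about 9 points, and MMPS already has an observed-data analysis. Both points stand. But the error is systematic, sampling noise does not cancel it, and the MMPS check does not reach the other endpoints.

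A reader might also infer that imputed volumes make the late ANCOVA standard errors too small. The visible volume ANCOVA is tied to Day 90, and no later one is explicit. Nor can a separate duration analysis be excluded: the list of other efficacy endpoints in Protocol 9.4.1.1 and the heading of SAP 9.3 are not visible.

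**Conclusion.** The concern holds in a limited form. The rule has no visit limit, late visits are tabulated, and the protocol's own account of a 3-month peak contradicts holding a Day 90 value constant to Day 180. The result can be an overstatement of persistence, chiefly at Day 180: about 1 to 4.5 points in the responder rate if all of the planned 10% dropout follows Day 90 with Day 90 as the last value, and about -0.5 to +3 points if dropout is spread evenly. Both ranges rest on assumed retention of 50% to 85%, assumed dropout timing, and leavers behaving like stayers.

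It would be wrong to read this as a threat to the main results. Every visible primary and secondary efficacy endpoint is at Day 90, and a value carried forward after Day 90 cannot enter them. The point is worth correcting because the rule conflicts with the stated time course and the change is cheap.

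**What to change.** In Protocol 9.4.1 and SAP 9.0, state that carry-forward applies only to visits through Day 90, leaving the Day 90 analyses as planned. For Days 120, 150 and 180:

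- Report all responder endpoints (MMPS, MMPS-P and PSAC) on observed data, with the number assessed per arm.
- Summarise lower facial volume on observed data, or with a repeated-measures model using the planned factors (study intervention, investigator site) and covariate (baseline MMPS grade).
- If missing is also counted as non-response, label it a conservative bound, because it errs against the arm with more responders.

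The cost is a sentence in each document plus minor programming. Late-visit denominators become slightly smaller, and late BOTOX results may look slightly less favourable. Observed-data rates still assume that leavers resemble stayers, so the number and timing of exits by arm should be shown beside them. Sample size, the Day 90 analyses and trial conduct do not change.
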